## **Participants:**

Eighty infertile patients undergoing IVF/ICSI are randomized to either RECO-18 treatment or multi-vitamins with the ratio of 1:1.

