### 5.5 The measurement of research results

Primary indicator: the ongoing pregnancy rate at 12 weeks' gestation.

Secondary indicators: the number of oocytes retrieved, the normal fertilization rate and the rate of high quality embryos, implantation rate, clinical pregnancy rate, and early miscarriage rate.

Randomization: randomized envelope method is used in the study. Random sequence is firstly generated by an independent statistician, secondly the grouping is randomized according to

random number and put into an opaque sealed envelope by the independent personnel, at last the investigator divides the subjects in line with the sealed envelope.

Random ratio: 1:1

Grouping: the treatment group takes RECO-18 while the control group takes the multi-vitamins.

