c. Oocyte retrieval, luteal support and embryo transfer: oocyte recovery is performed 34 to 38 hour after the trigger. Luteal support is provided on the day of oocyte retrieval, with vaginal micronized progesterone capsules (600mg/day) combined with oral dydrogesterone (30mg/day) until the pregnancy test. With the use of conventional IVF or ICSI fertilization, 1 to 2 cleavage stage embryos or day 5 blastocysts are transferred to the uterus, and the rest available embryos are cryopreserved.

d. If fresh embryo transfer is cancelled due to medical reasons, pregnancy outcome of the first thawed embryo transfer is collected. The endometrial preparation, thawed embryo transfer and luteal support are based on the routine operation.

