#### 5.8.7 Follow-up:

A total of three visits are followed up during the treatment procedure.

a. At the 14th day after embryo transfer: to record urinary pregnancy test, serum HCG and progesterone level.

If pregnancy test is positive, the following follow-up continues, otherwise it discontinues.

b. Four to five weeks after embryo transfer: to perform transvaginal ultrasound. Clinical pregnancy is defined as a gestational sac and fetal heart beat detected on ultrasound.

c. At 12 weeks' gestation: to perform ultrasound. Ongoing pregnancy is defined as live fetuses detected on ultrasound.

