#### 7.2 Analysis of primary indicator and secondary indicators:

Analysis of primary indicator: the two-sample rate test is used to compare the ongoing pregnancy rate at 12 weeks' gestation in the treatment group and the control group. Categorical variable is compared between groups using Pearson chi-squared test or Fisher's exact probabilistic method. Based on the FAS, the primary endpoint calculates the ongoing pregnancy rate at 12 weeks' gestation and its 95% confidence interval. Logistic regression is used to analyze the baseline effects, and the adjusted factors included age, infertility length, BMI, AMH, AFC, ovulation stimulation protocol, etc.

Analysis of secondary indicators: measurement data are compared using independent sample test or nonparametric analysis, and categorical variables are compared using Pearson chi-squared test or Fisher's exact probabilistic method between groups. Measurement data are analyzed by covariance analysis, and qualitative indicators are analyzed by Logistic regression to evaluate the baseline effects. Adjusted factors refer to the analysis of primary indicators.

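### Section 7.2 fixes no unit of analysis for the fertilisation, high-quality-embryo and implantation rates, so it permits, without committing to it, a pooled test whose P values are too small if a woman's results are positively correlated

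*Combined protocol and SAP*

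**What the plan says.** The woman is the randomised unit: "Eighty infertile patients undergoing IVF/ICSI are randomized to either RECO-18 treatment or multi-vitamins with the ratio of 1:1". Section 5.5 lists among the secondary outcomes "the normal fertilization rate and the rate of high quality embryos, implantation rate", with no numerator, denominator or unit. The only pregnancy endpoints defined are in Section 5.8.7, for example "Clinical pregnancy is defined as a gestational sac and fetal heart beat detected on ultrasound", and ongoing pregnancy at 12 weeks.

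Section 7.2 gives two routes for secondary outcomes:

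- Continuous data: "measurement data are compared using independent sample test or nonparametric analysis", with covariance analysis for adjustment.
- Categorical data: "categorical variables are compared using Pearson chi-squared test or Fisher's exact probabilistic method between groups", and for adjustment "qualitative indicators are analyzed by Logistic regression to evaluate the baseline effects".

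The covariates are those of the primary analysis: "the adjusted factors included age, infertility length, BMI, AMH, AFC, ovulation stimulation protocol, etc". On the number of embryos placed, Section 5.8.5 c says that "1 to 2 cleavage stage embryos or day 5 blastocysts are transferred to the uterus". Section 7 applies P<0.05 to all comparisons.

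**The concern.** A woman can contribute several oocytes and embryos, and up to two transferred embryos. These share her age, ovarian reserve, stimulation and partner, so their results may be correlated. The plan calls the three outcomes rates, and the only rate whose analysis it spells out, ongoing pregnancy, goes to a two-sample rate test with chi-squared or Fisher. An analyst could follow that pattern and put all oocytes or embryos from each arm into one 2×2 table. The test would then count oocytes as if each had been randomised.

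What is at stake is a false claim about oocytes or embryos. The background (Section 2) names oocyte and embryo quality as part of the exploratory question of this pilot, so a spuriously small P value there could be read as support for the proposed mechanism. Nothing later in the plan closes the gap. Section 7.1 leaves the definition of major protocol violations to be settled before lock, and Section 7.4.4 settles the analysed data set, but neither settles the unit.

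**Working it through.** **Inputs.** From the documents: 40 women per arm (Sections 5.1 and Research procedure), nominal level 5% (Section 7; two-sided is assumed), and at most two embryos transferred (Section 5.8.5 c). Not in the documents, and therefore assumed: intraclass correlation (ICC) 0 to 0.2; a mean of 10 oocytes and 5 to 7 embryos per woman; coefficient of variation (CV) of those counts 0 or 0.5; event rates of 70% (fertilisation) and 40% (embryo quality, implantation). The plan states no figure on this point, so there is none to reproduce.

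**Formulas.** For a mean of m units per woman, the design effect is DE = 1 + (m(1 + CV²) − 1) × ICC. The true two-sided error of a pooled nominal 5% test is 2(1 − Φ(1.96/√DE)).

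**Fertilisation and embryo quality.** Example: m = 10, CV = 0.5, ICC = 0.1 gives DE = 1 + (10 × 1.25 − 1) × 0.1 = 2.15. Then 1.96/√2.15 = 1.337, and the true error is 18.1%.

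| Assumption | ICC 0 | 0.05 | 0.1 | 0.2 |
|---|---|---|---|---|
| Oocytes, m = 10, CV 0: DE | 1 | 1.45 | 1.90 | 2.80 |
| true error | 5.0% | 10.4% | 15.5% | 24.2% |
| Oocytes, m = 10, CV 0.5: DE | 1 | 1.575 | 2.15 | 3.30 |
| true error | 5.0% | 11.8% | 18.1% | 28.1% |
| Embryos, m = 5, CV 0: DE | 1 | 1.20 | 1.40 | 1.80 |
| true error | 5.0% | 7.4% | 9.8% | 14.4% |
| Embryos, m = 7, CV 0.5: DE | 1 | 1.3875 | 1.775 | 2.55 |
| true error | 5.0% | 9.6% | 14.1% | 22.0% |

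**Implantation.** Here DE = 1 + (E[N²]/E[N] − 1) × ICC, with N the number of embryos transferred. If half the women receive two, E[N²]/E[N] = 2.5/1.5 = 1.667. At ICC 0.2, DE = 1.133 and the error is 6.6%. If all receive two, DE = 1.2 and the error is 7.4%. At ICC 0.05 the figures are 5.4% and 5.6%.

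**Simulation check.** Beta-binomial data under the null, 40 women per arm and CV 0.5, agree with the formula. At ICC 0 / 0.05 / 0.1 / 0.2 the pooled chi-squared error was 5.3 / 11.3 / 18.1 / 28.0% for fertilisation (mean 10) and 4.9 / 10.0 / 14.2 / 21.9% for embryo quality (mean 7). A separate run gave 29% for fertilisation at ICC 0.2. A t-test on one proportion per woman stayed at 4.6-5.4%. For implantation, logistic GEE clustered on woman stayed at 5.0-5.5%.

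**Power of the two valid routes.** For a 10-point difference under the same assumptions:

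| Outcome and method | ICC 0 | 0.05 | 0.1 | 0.2 |
|---|---|---|---|---|
| Fertilisation, per-woman t-test | 78% | 67% | 58% | 45% |
| Fertilisation, cluster-robust pooled proportions | 90% | 74% | 61% | 44% |
| Embryo quality, per-woman t-test | 52% | 45% | 39% | 32% |
| Embryo quality, cluster-robust pooled proportions | 66% | 53% | 43% | 33% |

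**The case against.** The strongest reply is that this is a silence, not a stated error. The harm needs two things that the documents do not establish: that oocytes or embryos are pooled, and that results within a woman are positively correlated. The text arguably leans the other way. The analysis sets in Section 7.1 are sets of subjects, and most of the listed covariates (age, BMI, AMH, AFC) belong to the woman. One proportion per woman, treated as measurement data, fits Section 7.2 and is valid. All of this stands. A reader might infer that the plan prescribes pooled oocyte tests; it does not.

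The size is also assumption-driven. Only the 40 per arm, the 5% level and the limit of two embryos come from the documents. The trial excludes expected or previous poor responders and polycystic ovarian syndrome, which may narrow the spread of oocyte counts and make a CV of 0.5 too high. That moves the figures towards the equal-size rows, but at ICC 0.1 and 10 oocytes the error is still about three times nominal (15.5%).

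Implantation is a weak example, because at most two embryos are transferred. Finally, the unweighted per-woman t-test is one valid choice among several and can cost power, so it should not be imposed as the only remedy. Both points are accepted.

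What the reply does not remove is that the invalid route is permitted and nothing requires the choice to be made before the results are seen.

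**Conclusion.** The point holds as an ambiguity that should be closed. Section 7.2 permits an analysis of three secondary outcomes that is invalid under positive within-woman correlation, and does not commit to it. If pooling is used, the true error of a nominal 5% test is roughly 10-29% for fertilisation and 7-22% for embryo quality over ICC 0.05 to 0.2, and about 5-7% for implantation over ICC up to 0.2. At ICC 0 there is no inflation. These figures show direction and range under assumed ICC, counts and event rates; they do not estimate the error in this trial.

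A reader might also infer that the trial's main conclusion is at risk. It is not: ongoing pregnancy at 12 weeks is one result per woman, and the formal purpose in Section 3 concerns pregnancy outcomes. The weight is that of a secondary-outcome problem in a self-described pilot: worth fixing, but not a threat to the primary analysis.

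**What to change.** - **Section 7.2:** state that the woman is the independent unit for these three rates, and that pooled chi-squared, Fisher or ordinary logistic tests on oocytes or embryos will not be used.
- **Pre-specify one cluster-valid method before database lock:** either (a) logistic GEE, or a comparison of pooled proportions, with standard errors clustered on woman, for all three rates; or (b) one proportion per woman, compared by the t-test and covariance analysis already named.
- **Section 5.5:** give each rate's numerator and denominator, for example normally fertilised oocytes over oocytes inseminated or injected.
- **Reporting:** give by arm the number of women with no oocyte, embryo or transfer, since they have no value for the rate.

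The cost is wording, plus one added method if (a) is chosen; no extra patients or data are needed. P values may become less favourable. Under the assumed values, option (b) gives up about 7 to 12 points of power for fertilisation at ICC 0.05 to 0 (74 − 67 = 7; 90 − 78 = 12), a loss that disappears by ICC 0.2. Option (b) also describes the average woman and not the average oocyte. The two can differ if oocyte number, itself a secondary outcome, is related to the rate.

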#### 7.3 Safety indicators

Use descriptive statistics to summarize laboratory examination and vital signs as safety evaluation indicators, and summarize the changes of each index relative to the baseline. The indexes are classified as normal or abnormal (without clinical significance), and calculated the case number and percentage in each classification. Other safety indicators are summarized or listed as appropriate.

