### 5.4 Exit criteria

1) Patients request to drop out; 2) the cycle is cancelled due to low ovarian response or premature ovulation; 3) actual treatment deviates from the protocol; 4) patients lost follow-up.

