#### 5.6 Informed consent

Before the initiation of study, the informed consent form (ICF) should be used to inform the potential subjects of benefits and risks in simple language. ICF should specify that the informed consent is signed voluntarily, and the potential benefits and risks associated with study are specified, and subjects may drop out from the study at any time.

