## 6. Safety evaluation

6.1 Adverse events: Any adverse medical events occurring during the study period are defined as adverse events, such as drug reactions, adverse reactions associated with ovarian stimulation, complications associated with pregnancy, and other discomfort complaints

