#### 6.2 Adverse events report:

Mild adverse events are recorded in the progress note.

Serious adverse events are submitted to Medicine Ethics Committee within 48 hours of occurrence.

6.3 Safety indexes are adverse events occurring in the treatment group and the control group, such as gastrointestinal reactions and allergies.

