### 7.4.4 Data audit and database locking

After all questions of the data in the system are resolved, the principal investigator, statistician and data administrator first review the data and determine the association of adverse events and study, then determine the analyzed data set, last lock the audited data without any change. If there is any question after the database lock, it should be corrected in the statistical analysis process, and be recorded in detail.

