9.3 Risk control measures

9.3.1 Subjects are fully informed and sign informed consent before participation.

9.3.2 If serious adverse events occur, stop the study immediately and report to the department and Medicine Ethics Committee in the first time, and control the impact of adverse events to a minimum.

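### Section 7.3 gives clinically significant laboratory and vital-sign abnormalities no class; secondarily, 9.3.2 leaves unclear what a serious adverse event stops

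*Combined protocol and SAP*

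**What the plan says.** **Classification of safety results.** Section 7.3 plans descriptive statistics and change from baseline for laboratory tests and vital signs. It then gives the rule for the categorical table: "The indexes are classified as normal or abnormal (without clinical significance), and calculated the case number and percentage in each classification". Its closing sentence leaves other safety indicators to be summarised or listed as seems fit.

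**Adverse events.** Section 6.1 defines these broadly and gives examples that include "adverse reactions associated with ovarian stimulation, complications associated with pregnancy". Section 6.2 sets the reporting time: "Serious adverse events are submitted to Medicine Ethics Committee within 48 hours of occurrence". Section 6.3 adds: "Safety indexes are adverse events occurring in the treatment group and the control group, such as gastrointestinal reactions and allergies". The visit schedule collects adverse events at V2 to V6.

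**Stopping.** Section 9.3.2 reads: "If serious adverse events occur, stop the study immediately and report to the department and Medicine Ethics Committee in the first time". The sentence ends by asking that the impact of adverse events be kept small. Section 5.4 gives four exit criteria: patient request, a cancelled cycle, and "actual treatment deviates from the protocol; 4) patients lost follow-up". Section 5.6 requires the consent form to say that "subjects may drop out from the study at any time".

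**Biochemistry.** Section 5.8.3 lists a panel that includes ALT, AST and creatinine, without naming a visit.

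**The concern.** The per-arm table in 7.3 is the plan's only categorical summary of laboratory and vital-sign safety, and as worded it leaves out the category of most interest. A programmer who follows the text must either drop a clinically significant result from the count or place it in a class whose label denies its significance. In both cases the arms cannot be compared on it.

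The stop instruction raises a separate question of conduct. Its trigger is a term that the plan does not define, and its object, the study, could mean one woman's participation or the whole trial. Two investigators facing the same event could act differently, and both could claim to be following 9.3.2.

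**Working it through.** No stated figure is in question, so the check sets the sections side by side and counts.

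**1. Classes in 7.3.** Named: normal; abnormal without clinical significance. That is 2. The possible states of a result are normal (a women), abnormal and not significant (b), and abnormal and significant (c), with n = a + b + c measured. The table as written reports a/n and b/n, which sum to 1 − c/n. The quantity c/n, the one of interest, is not tabulated. If all 40 women in a group are in the safety set, each woman in c is 1/40 = 2.5% of that arm.

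No other section supplies the missing class. The last sentence of 7.3 concerns other indicators. Sections 6.1 to 6.3 cover adverse events, and none of them requires a clinically significant value to be recorded as one.

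**2. Stopping in 9.3.2.**

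| Section | What it settles | What it leaves open |
|---|---|---|
| 9.3.2 | Serious events, without restriction, lead to a stop and a report | Whether the participant or the trial stops |
| 6.1 | Stimulation reactions and pregnancy complications are adverse events | What makes an event serious |
| 6.2 | Reporting within 48 hours | What makes an event serious; whether anything stops |
| 5.4 | Four grounds for individual exit | Serious events are not named |

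Taken literally, 9.3.2 and 6.1 together mean that a single serious event in either arm, including a background complication of IVF or pregnancy, would halt the trial. Taken as guidance on managing the affected woman, which the end of the sentence also fits, they mean something much narrower. The text does not choose between the two. The documents give no serious-event rate, so the chance of the literal trigger cannot be calculated.

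**3. Biochemistry.** Section 5.8.3 lists ALT, AST, creatinine, TC, TG, HDL, LDL, ApoB, Hs-CRP, fasting glucose and fasting insulin: 11 tests. The visit schedule has 10 rows: consent, eligibility, personal information, history, medication, physical examination, vital signs, sex hormones, ultrasound and adverse events. None covers the panel. A change from baseline needs a later measurement. Vital signs and sex hormones have one (V1 to V3), but no later measurement is shown for the 5.8.3 panel. Section 7.3 does not say whether its laboratory results include that panel.

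**The case against.** **On 7.3.** The wording is very likely a slip. Adverse events are defined broadly, collected at V2 to V6 and reported for both groups, so a significant abnormality could surface there. This stands in part. A reader might infer that such findings would be lost to the trial, and the documents do not support that. But recording a laboratory value as an adverse event is an inference, since 6.1 gives no laboratory example, and the 7.3 table would still omit the class.

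**On 9.3.2.** A reader might infer that the passages contradict one another. They do not do so outright: reporting within 48 hours under 6.2 is compatible with stopping and reporting promptly under 9.3.2, and patient request, protocol deviation or the freedom to leave in 5.6 could cover a woman who stops. A reader might also take section 7.4.4, where the pre-lock review is to "determine the association of adverse events and study, then determine the analyzed data set, last lock the audited data", as proof that relatedness is judged only at that point, so that an immediate stop could never be limited to related events. That does not follow. Section 7.4.4 says that the judgement is made at that review, not that it is made nowhere else. What stands is one undefined term and one ambiguous object.

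**On 5.8.3.** A reader might infer from the absence of a basal label that no baseline sample is planned. The evidence is too thin. Section 5.8.4 is also unlabelled, yet 7.2 adjusts for the antral follicle count it collects as a baseline factor, and 5.8.1 to 5.8.4 read as one work-up before stimulation. Only the absence of a scheduled later measurement stands, and it matters only if 7.3 is meant to include the panel.

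**Conclusion.** The point holds as a correction to safety reporting. Section 7.3 names 2 of the 3 classes needed, and a table built as written cannot show how many women in each arm had a clinically significant laboratory or vital-sign abnormality. This rests on reading the sentence as it stands; if with or without was meant, the correction is purely one of wording, but it is still needed because the table would be programmed from this text.

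The ambiguity in 9.3.2 is real but secondary: serious is undefined, and the scope of the stop is unclear. The biochemistry item is a minor clarification. None of the three affects the primary-outcome analysis in 7.2, and no figure in the plan is shown to be wrong.

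**What to change.** 1. In 7.3, tabulate three classes by arm: normal; abnormal, not clinically significant; abnormal, clinically significant. The cost is one table category, plus a clinical-significance field on the case report form if it has none.
2. The investigators and the ethics committee should reconcile 9.3.2 with 6.1, 6.2 and 5.4, so that the plan says what serious means and what is stopped. The content is theirs to decide. The cost is protocol wording.
3. State whether the laboratory results in 7.3 include the 5.8.3 panel, and report change from baseline only for indexes that have a later measurement. If the panel is meant to be included, its measurement times must be given. Narrowing the change summary to vital signs and sex hormones would make the text consistent, but it would leave out the liver and kidney tests, so it should not be adopted merely for tidiness. Stating the scope costs one sentence; any added sampling would be a separate decision for the investigators.

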## 7.4 Data management and quality control

### 7.4.1 Database establishment

The Epidata electronic database is established based on the case report form before the initiation of study.

### 7.4.2 Data filling and review

Case report forms should be filled by designated, trained researchers with uniform regulation. Project principal assigns the researcher to review the completeness and accuracy of the case report form, and guide the researcher to make any necessary corrections or additions. When the data are questionable, fill in the data query form, and the researcher should respond the question and confirm the correction. Keep the signed data query form.

